6.1.1. Description of Dose Selection

Pharmacokinetic, PD, and safety data from Part A of the study will be used to determine the dose for Part B and the final dose for Part C. This will occur when PK, PD, and safety data from Part A have been sufficiently analyzed and reviewed at a Dose Determination Review meeting. This meeting will be led by a designated member of the Regeneron clinical team (generally either the medical director/study director or the clinical study lead) and at a minimum will be attended by the Regeneron Medical Monitor and the Risk Management Lead or designee; other individuals, including the Clinical Pharmacology Lead, may be included. The final dose selected will not exceed evinacumab 20 mg/kg.

6.1.2. End of Study Definition

The end of study is defined as the date of the last visit of the last patient.

6.2. Planned Interim Analysis

No interim analysis is planned.

6.3. Study Committees

6.3.1. Independent Data Monitoring Committee

An independent data monitoring committee (IDMC) composed of members who are independent from the sponsor and the study investigators, will monitor patient safety by conducting formal reviews of accumulated safety data; if requested, the IDMC may have access to any other requested data for the purposes of a risk-benefit assessment.

The IDMC will provide the sponsor with appropriate recommendations on the conduct of the clinical study to ensure the protection and safety of the patients enrolled in the study. The IDMC will also institute any measures that may be required for ensuring the integrity of the study results during the study execution.

All activities and responsibilities of the IDMC are described in the IDMC charter.

7. SELECTION, WITHDRAWAL, AND REPLACEMENT OF PATIENTS

7.1. Number of Patients Planned

For Part A, approximately 6 patients are planned. If data from 6 patients is insufficient, up to 4 more patients may be enrolled to confirm the dose in Part B.

For Part B, approximately 14 patients are planned. Patients for Part B will not include patients from Part A. Patients from Part A and Part B may enter Part C.

7.1.1. Rescreening of Patients

Patients who do not meet eligibility criteria during the initial screening may rescreen. Patients who are rescreened after the screening window ends must re-consent for study participation and repeat all screening procedures.

Patients who do not meet all eligibility criteria during the initial screening, and are still within the screening window, may retest those assessments that did not meet eligibility criteria.

7.2. Study Population

Males and females age 5 through 11 years, diagnosed with HoFH receiving any combination of lipid-lowering therapies (additional information on background therapies provided in Section 6.1).

HoFH diagnosis can be confirmed by either the genetic or clinical criteria shown in Section 7.2.1.

7.2.1. Inclusion Criteria

A patient must meet the following criteria to be eligible for inclusion in the study:

1. Males and females ages 5 to 11 years at the time of the screening visit
2. Diagnosis of functional HoFH by either genetic or clinical criteria:

Genetic Criteria

- a. Documented functional mutation or mutations in both LDLR alleles
Note: Patients who have null receptor mutations on both LDLR alleles, ie, double null, are eligible
- b. Documented homozygous mutations in LDLRAP1, or homozygous or compound heterozygous mutations in APOB or PCSK9
Note: Patients who are double heterozygous, i.e. mutations on different genes [LDLR/PCSK9 or LDLR/APOB] are eligible

Clinical Criteria

- c. Untreated TC >500 mg/dL (>13 mmol/L) and triglycerides (TGs) <300 mg/dL (<7.8 mmol/L)

AND

Both parents with documented TC >250 mg/dL OR cutaneous or tendinous xanthoma in the study patient before age 10 years

3. LDL-C >130 mg/dL at the screening visit
4. Body weight \geq 15 kg
5. Receiving stable maximally tolerated therapy*at the screening visit

*Maximally tolerated therapy could include a daily statin.

Note: Patients who are not able to be on a maximum daily statin should be on the appropriate dose for the patient or no statin, according to the investigator's judgment. Some examples of acceptable reasons for a patient taking a lower statin dose include but are not limited to: adverse effects on higher doses, lack of efficacy, regional practices, local prescribing information, concomitant medications. The reason(s) will be documented in the case report form (CRF).

6. Willing and able to comply with clinic visits and study-related procedures
7. Parent(s) or legal guardian(s) must provide the signed informed consent form (ICF). Patients \geq 5 years of age (or above age determined by the IRB/EC and in accordance with the local regulations and requirements) must also provide informed assent forms (IAFs) to enroll in the study, and sign and date a separate IAF or ICF signed by the parent(s)/legal guardian(s) (as appropriate based on local regulations and requirements)

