In non-FH populations, numerous epidemiological studies and CV outcomes studies with lipid-lowering therapies have continually demonstrated that lowering LDL-C reduces the risk of CV events. In fact, the body of evidence from the statin literature shows that the relationship between LDL-C reduction and CV event reduction is approximately linear and for every 1 mmol/L (38.7 mg/dL) reduction in LDL-C there is a corresponding 22% risk reduction in CV events (Baigent, 2010). Moreover, results from recent outcomes trials with ezetimibe (IMPROVE-IT (Cannon, 2015)), alirocumab (ODYSSEY OUTCOMES (Schwartz, 2018)) and evolocumab (FOURIER (Sabatine, 2017)) reinforce this concept, providing additional evidence for the relationship between LDL-C lowering through diverse mechanisms and reductions in CV events. Within the context of this study in the HoFH pediatric patient population, additional reductions in LDL-C at an early age may get patients closer to their LDL-C target and maintaining these levels could translate into significant benefit in reducing CV risk.

It is also expected that treatment with evinacumab will be well tolerated and have an acceptable safety profile. The accumulated safety information from the most recent phase 2 and phase 3 studies where evinacumab was given IV in patients with HoFH (R1500-CL-1629, R1500-CL-1719) or persistent hypercholesterolemia (R1500-CL-1643) shows that the more common adverse events across all the studies include Nasopharyngitis, Rhinorrhoea, Upper respiratory tract infection, Influenza-like illness, Back pain, Pain in extremity, Dizziness, Headache, Nausea, Abdominal pain, and Fatigue.

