 - b. Considered by the investigator or any sub-investigator as inappropriate for this study for any reason, eg:
 - Deemed unable to meet specific protocol requirements, such as scheduled visits
 - Investigator or any sub-investigator, pharmacist, study coordinator, other study staff or relative thereof directly involved in the conduct of the protocol, etc.
 - Presence of any other conditions (eg, geographic or social), either actual or anticipated, that the investigator feels would restrict or limit the patient's participation for the duration of the study
12. Laboratory findings during screening period (not including randomization labs):
 - Positive urine pregnancy test in females of childbearing potential
 - Triglycerides >300 mg/dL (>4.52 mmol/L) (1 repeat lab is allowed)
 - Alanine aminotransferase (ALT) or aspartate aminotransferase (AST) >3 x upper limit of normal (ULN) (1 repeat lab is allowed)
 - CPK >3 x ULN (1 repeat lab is allowed)
13. Known hypersensitivity to monoclonal antibodies or any excipient in the evinacumab solution for infusion
14. Sexually active males, and sexually active females of childbearing potential at screening
15. Female patients who have commenced menstruating at any time during the study and are either:
 - Found to have a positive urine pregnancy test, or

- Sexually active, not using or not willing to use an established highly effective contraception method prior to subsequent dosing of study treatment, during the study, and for at least 24 weeks after the last dose of study drug. Highly effective contraceptive measures include:
 - Stable use of combined (estrogen- and progestogen-containing) hormonal contraception associated with inhibition of ovulation initiated 2 or more menstrual cycles prior to screening: oral, intravaginal, transdermal
 - Stable use of progestogen-only hormonal contraception associated with inhibition of ovulation initiated 2 or more menstrual cycles prior to screening: oral, injectable, implantable
 - Intrauterine device or intrauterine hormone-releasing system
 - Bilateral tubal ligation
 - Vasectomized partner. Note: vasectomized partner is a highly effective birth control method provided that the partner is the sole sexual partner of the WOCBP trial participant and that the vasectomized partner has received medical assessment of the surgical success

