Total-C, HDL-C, Apo B, Apo A-1, TG, and Lp(a) will be directly measured by the central laboratory. LDL-C will be calculated using the Friedewald formula. If TG values exceed 400 mg/dL (4.52 mmol/L) or if calculated LDL-C values are below 25 mg/dL (0.65 mmol/L), LDL-C will be measured via the beta quantification method (rather than via the Friedewald formula). Non-HDL-C will be calculated by subtracting HDL-C from the TC.

Detailed procedures of sample preparation, storage, and shipment are provided in the laboratory manual.

9.2.2.1. **Lipid Panel**

Fasting (at least 8 hours) blood samples will be collected at specified time points shown in Section 9.1 for assessment of the lipid profile, comprising calculated LDL-C, HDL-C, non-HDL C, TC, and TGs. These samples will also be used for specialty lipid panel assessment when it is scheduled at the same time as the lipid panel assessment.

9.2.2.2. **Specialty Lipid Panel**

Fasting (at least 8 hours) blood samples will be collected at specified time points shown in Section 9.1 for assessment of the specialty lipid profile, comprising Apo B, Apo A-1, ratio of Apo B/Apo A-1, ApoCIII, ApoE, and Lp(a). The specialty lipid panels will be assessed in the same sample that is collected for the lipid panel.

9.2.3. **Safety Procedures**

9.2.3.1. **Vital Signs**

Vital signs, including temperature, sitting blood pressure, pulse, and respiration rate, will be collected predose at time points according to [Table 1](#), [Table 2](#), and [Table 3](#).

On dosing days, vital signs consisting of blood pressure and pulse rate will also be collected pre-dose and 30 minutes and 60 minutes after completion of the IV infusion.

Blood pressure should be measured in the same arm throughout the study after the patient has been resting quietly for at least 5 minutes. Pulse rate will be measured at the time of the measurement of blood pressure.

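### The triglyceride eligibility limits have inconsistent SI equivalents: 300 mg/dL is paired with both 7.8 and 4.52 mmol/L, so a reader working in mmol/L could apply a looser limit

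*Protocol*

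**What the plan says.** Three places in the protocol give a triglyceride (TG) threshold in both units.

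- **Section 7.2.1, inclusion 2c** (the clinical route to the HoFH diagnosis): "triglycerides (TGs) <300 mg/dL (<7.8 mmol/L". The cholesterol condition in the same line is "Untreated TC >500 mg/dL (>13 mmol/L".
- **Section 7.2.2, exclusion 12** (screening laboratory findings, all patients): "Triglycerides >300 mg/dL (>4.52 mmol/L) (1 repeat lab is allowed".
- **Section 9.2.2, Efficacy Procedures** (the switch from the Friedewald formula to beta quantification): "If TG values exceed 400 mg/dL (4.52 mmol/L".

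For cholesterol, Section 3.3 gives a conversion of its own: "every 1 mmol/L (38.7 mg/dL) reduction in LDL-C". No section of the protocol or SAP says whether mg/dL or mmol/L governs eligibility.

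**The concern.** One mg/dL value has two SI equivalents, and one SI value has two mg/dL equivalents. A conversion between units is a fixed multiple for a given analyte, so these pairs cannot all hold.

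Two of the three are eligibility limits. In mg/dL they coincide at 300, apart from a value of exactly 300. In mmol/L they are 7.8 and 4.52. The study is planned for about 24 sites across regions such as Europe, North America and Asia (Synopsis), so it is plausible, though not shown, that some sites work in mmol/L. Such a site could enrol a patient whom a site reading mg/dL would reject. What is at stake is uniform application of the entry criteria.

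**Working it through.** **Inputs.** TG pairs: 300 and 7.8 (inclusion 2c), 300 and 4.52 (exclusion 12), 400 and 4.52 (Section 9.2.2). Cholesterol pairs: 500 and 13 (inclusion 2c), 25 and 0.65 (Section 9.2.2), and 38.7 mg/dL per mmol/L (Section 3.3).

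**Step 1: implied factor = mg/dL ÷ mmol/L.** The last column allows half a unit in the last printed digit of the mmol/L figure.

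| Place | Analyte | Calculation | Factor | Range from rounding |
|---|---|---|---|---|
| Inclusion 2c | TG | 300 / 7.8 | 38.46 | 300/7.85 to 300/7.75 = 38.2 to 38.7 |
| Exclusion 12 | TG | 300 / 4.52 | 66.37 | 300/4.525 to 300/4.515 = 66.3 to 66.4 |
| Section 9.2.2 | TG | 400 / 4.52 | 88.50 | 400/4.525 to 400/4.515 = 88.4 to 88.6 |
| Inclusion 2c | Total cholesterol | 500 / 13 | 38.46 | – |
| Section 9.2.2 | LDL-C | 25 / 0.65 | 38.46 | – |

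The three TG ranges do not overlap, so rounding is not the explanation.

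**Step 2: where the figures may come from.** The TG factor in 2c equals the two cholesterol factors in the table. With the Section 3.3 factor, 300 / 38.7 = 7.75, which rounds to 7.8. It looks like a cholesterol conversion applied to triglycerides. The 4.52 in exclusion 12 is the figure that Section 9.2.2 attaches to 400 mg/dL.

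**Step 3: choice of reference.** Section 9.2.2 prints a TG pair and a cholesterol pair in one sentence with different factors (88.50 and 38.46). It is therefore the one place that visibly treats the two analytes separately, and I take its TG factor as reference.

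**Step 4: sizes at 88.50 mg/dL per mmol/L.**

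- 300 / 88.50 = 3.39 mmol/L. Neither printed SI limit reproduces this.
- Inclusion 2c: 7.8 × 88.50 = 690 mg/dL, and 690 / 300 = 2.30. Values from 300 to just below 690 mg/dL fail in mg/dL and pass in mmol/L.
- Exclusion 12: 4.52 × 88.50 = 400 mg/dL, and 400 / 300 = 1.33. Values above 300 and up to 400 mg/dL are excluded in mg/dL and eligible in mmol/L.
- Between the two SI limits: 7.8 / 4.52 = 1.73.

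**Step 5: dependence on the reference.** If the exclusion 12 pair were right instead, 7.8 mmol/L would be 7.8 × 66.37 = 518 mg/dL. If the 2c pair were right, 4.52 mmol/L would be 4.52 × 38.46 = 174 mg/dL, which is stricter than 300. The contradiction holds under any choice; the sizes in Step 4, and the statement that both SI limits are looser, rest on Section 9.2.2.

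**The case against.** The best case against is that this is an editorial slip with little practical reach.

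- **Exclusion 12 caps screening triglycerides for everyone.** Even read in mmol/L, it stops at 400 mg/dL on the reference used here. If the 2c value is the screening value, the 7.8 figure admits nobody whom exclusion 12 would not already stop. This stands. The 690 mg/dL figure is correct for 2c taken alone, but it has practical effect only if the 2c value is a separate, earlier one. That is plausible: the criterion refers to untreated total cholesterol, while inclusion 5 requires stable maximally tolerated therapy at screening. It remains an assumption, because the protocol states neither the source of the 2c value nor whether untreated also covers the triglycerides.
- **300 mg/dL appears in both criteria and is printed first.** Inclusion 3 is in mg/dL only, and SAP Section 5.7 runs the lipid models in conventional units. This makes 300 mg/dL the more natural reading, but it does not settle exclusion 12, whose SI figure is exactly the one the protocol elsewhere attaches to 400 mg/dL.
- **Central measurement.** Section 9.2.2 says "TG, and Lp(a) will be directly measured by the central laboratory", which limits differences between sites. It fixes the measured value, however, and not the limit applied to it. Section 9.1 also allows local laboratories during the COVID-19 emergency.
- **2c concerns only one diagnostic route.** Section 7.2 says "HoFH diagnosis can be confirmed by either the genetic or clinical criteria", and a patient on the clinical route must also meet the cholesterol condition and either the parental-cholesterol or the xanthoma condition. Genotyping is mandatory (Section 9.2.7.2), so a doubtful clinical-route entry should show in the data. This narrows the affected group but does not correct the criterion.
- **LDL-C measurement.** Above 400 mg/dL, LDL-C is measured by beta quantification, so the loosest reading of exclusion 12 ends where that safeguard begins. I agree, and I claim no effect on the primary estimate.

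**Conclusion.** The concern holds. At most one of the three triglyceride pairs can be right, and the two eligibility criteria contradict each other in mmol/L. With Section 9.2.2 as reference, both printed SI limits are looser than the mg/dL limits beside them: 2.3 times in inclusion 2c and 1.33 times in exclusion 12. For a screening value the effective ambiguity is 300–400 mg/dL. The wider range, up to 690 mg/dL, matters only where 2c was judged on a value from before screening.

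No site is shown to have used the mmol/L figures, and the documents do not allow a count of affected patients. This should be fixed because the figures are operative entry limits, but it does not threaten the trial's main result.

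**What to change.** Reconcile inclusion 2c, exclusion 12 and Section 9.2.2 so that each mmol/L figure is the arithmetic equivalent of the mg/dL figure beside it. The sponsor should confirm which limit was intended in each criterion; the documents do not decide this and I do not propose a value. Add one sentence stating which unit governs eligibility.

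Then check the triglyceride records of enrolled patients against the reconciled limits, starting with anyone who qualified under 2c.

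The cost is a protocol clarification of two figures and one sentence, plus a record check for about 20 patients (6 planned in Part A and 14 in Part B, Protocol Section 11.2).

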7.2.2. Exclusion Criteria

A patient who meets any of the following criteria will be excluded from the study:

1. Background pharmacologic LMT, nutraceuticals or over-the-counter (OTC) therapies known to affect lipids, at a dose/regimen that has not been stable for at least 4 weeks (8 weeks for PCSK9 inhibitors) before the screening visit and patient is unwilling to enter the run-in period
2. For patients entering Part A, unable to temporarily discontinue apheresis from the baseline visit through the week 4 visit
3. Receiving lipid apheresis, a setting (if applicable) and schedule that has not been stable for approximately 8 weeks before the screening visit or an apheresis schedule that is not anticipated to be stable over the duration of the treatment period (48 weeks). A stable schedule is defined as a weekly (every 7 ± 1 days) or every other week (every 14 ± 2 days) schedule
4. Plasmapheresis within 8 weeks of the screening visit, or plans to undergo plasmapheresis during Part A or Part B
5. Presence of any clinically significant uncontrolled endocrine disease known to influence serum lipids or lipoproteins
6. Newly diagnosed (within 3 months prior to randomization visit [week 0/day 1]) diabetes mellitus or poorly controlled (hemoglobin A1c [HbA1c] >9%) diabetes

7. Chronic use of systemic corticosteroids, unless used as replacement therapy for pituitary/adrenal disease with a stable regimen for at least 6 weeks prior to randomization
Note: topical, intra-articular, nasal, inhaled and ophthalmic steroid therapies are not considered as 'systemic' and are allowed
8. History of a myocardial infarction (MI), percutaneous coronary intervention (PCI), uncontrolled cardiac arrhythmia, carotid surgery or stenting, stroke, transient ischemic attack (TIA), valve replacement surgery, carotid revascularization, endovascular procedure or surgical intervention for peripheral vascular disease within 3 months prior to the screening visit
9. History of cancer within the past 5 years
10. Use of any active investigational drugs within 1 month or 5 half-lives, whichever is longer
11. Conditions/situations such as:
 - a. Any clinically significant abnormality identified at the time of screening that, in the judgment of the investigator or any sub-investigator, would preclude safe completion of the study or constrain endpoints assessment; eg, major systemic diseases, patients with short life expectancy
 - b. Considered by the investigator or any sub-investigator as inappropriate for this study for any reason, eg:
 - Deemed unable to meet specific protocol requirements, such as scheduled visits
 - Investigator or any sub-investigator, pharmacist, study coordinator, other study staff or relative thereof directly involved in the conduct of the protocol, etc.
 - Presence of any other conditions (eg, geographic or social), either actual or anticipated, that the investigator feels would restrict or limit the patient's participation for the duration of the study
12. Laboratory findings during screening period (not including randomization labs):
 - Positive urine pregnancy test in females of childbearing potential
 - Triglycerides >300 mg/dL (>4.52 mmol/L) (1 repeat lab is allowed)
 - Alanine aminotransferase (ALT) or aspartate aminotransferase (AST) >3 x upper limit of normal (ULN) (1 repeat lab is allowed)
 - CPK >3 x ULN (1 repeat lab is allowed)
13. Known hypersensitivity to monoclonal antibodies or any excipient in the evinacumab solution for infusion
14. Sexually active males, and sexually active females of childbearing potential at screening
15. Female patients who have commenced menstruating at any time during the study and are either:
 - Found to have a positive urine pregnancy test, or

- Sexually active, not using or not willing to use an established highly effective contraception method prior to subsequent dosing of study treatment, during the study, and for at least 24 weeks after the last dose of study drug. Highly effective contraceptive measures include:
 - Stable use of combined (estrogen- and progestogen-containing) hormonal contraception associated with inhibition of ovulation initiated 2 or more menstrual cycles prior to screening: oral, intravaginal, transdermal
 - Stable use of progestogen-only hormonal contraception associated with inhibition of ovulation initiated 2 or more menstrual cycles prior to screening: oral, injectable, implantable
 - Intrauterine device or intrauterine hormone-releasing system
 - Bilateral tubal ligation
 - Vasectomized partner. Note: vasectomized partner is a highly effective birth control method provided that the partner is the sole sexual partner of the WOCBP trial participant and that the vasectomized partner has received medical assessment of the surgical success
 - only if defined as refraining from heterosexual intercourse during the entire period of risk associated with study treatments. True abstinence: When this is in line with the preferred and usual lifestyle of the patient. Periodic abstinence (calendar, symptothermal, post-ovulation methods), withdrawal (coitus interruptus), spermicides only, and lactational amenorrhea method (LAM) are not acceptable methods of contraception.
16. Male patients who become sexually active at any time during the study and do not use an established acceptable contraception method of consistent use of barrier contraception with spermicide during the study and for up to 24 weeks after the last infusion of study drug.
17. Individuals who are accommodated in an institution by official or court order.

